3.3 Modified Full Analysis Set

The **modified full analysis set (mFAS)** will be a subset of the FAS excluding all subjects for whom laboratory results did not confirm patient's eligibility, i.e. severe VWD type 1, 2A, 2B, 2M or 3 not confirmed.

Statistical Analysis Plan	Version 6.0		Page 9 of 24
Sponsor	Octapharma	Protocol No	WIL-31

3.4 Per Protocol Set

The **per-protocol (PP) set**, i.e. a subset of the FAS, will exclude subjects with major protocol deviations which may have an impact on the evaluation of the primary study outcome parameter (major protocol deviations as defined during DRM).

3.5 Surgery Set

The **surgery (SURG) set** will be a subset of the FAS, containing all subjects who underwent a surgical procedure treated with IMP prior to start of surgery during their Prophylactic Treatment Phase.

3.6 Pharmacokinetic Set

The **pharmacokinetic (PK) set** will be a subset of the FAS containing all subjects with a pharmacokinetic assessment.

3.7 Pharmacokinetic Per-Protocol Set

The **pharmacokinetic Per-Protocol (PK PP) set** will be a subset of the PK, excluding all subjects for whom laboratory results did not confirm patient's eligibility, i.e. severe VWD type 1, 2A, 2B, 2M or 3 not confirmed and excluding patients with an inhibitor to von Willebrand factor or factor FVIII at PK visit. Invalid samples/PK profiles (e.g. hemolyzed samples) will be excluded from PK-analysis as defined during DRM.

3.8 Subgroup analyses

The analyses of the efficacy endpoints 'efficacy of prophylactic treatment' and 'efficacy in treatment of breakthrough BEs' will be presented in the following subgroups:

- Age groups ('6 to 11, 12 to 16 and >16 years').
- VWD type ('severe type 1', 'type 2' and 'type 3')
- Sex ('Female', 'Male')
- Race, according to CDISC Controlled Terminology (dependent on the number of subjects per race)

The safety analysis will be presented by the following subgroup:

- Age groups ('6 to 11, 12 to 16 and >16 years').

Statistical Analysis Plan	Version 6.0		Page 10 of 24
Sponsor	Octapharma	Protocol No	WIL-31

4 STATISTICAL ANALYSES

All statistical analyses will be performed using the SAS® software (Version 9.4 or later). Pharmacokinetic parameters will be calculated using the WinNonlin software for Windows, version 7.0 or later using a non-compartment model (for definitions see section 8.1 of this SAP):

Descriptive statistics will always be given for the entire population.

The analysis of safety will be based on the SAF set.

Analysis of the primary endpoint will be performed on the FAS, mFAS and PP set, where the primary analysis set will be the mFAS.

For secondary and other endpoints (except endpoints regarding surgeries), FAS, mFAS and PP analyses will be carried out, unless the latter analysis sets differ by no more than 5% of patients in the mFAS.

Analysis of the efficacy and safety of *Wilate* in surgeries will be based on the SURG set.

If not stated otherwise the following standard descriptive statistics will be presented:

Descriptive statistics for continuous data

Number of subjects (N), arithmetic mean, standard deviation (SD), minimum, lower quartile, median, upper quartile and maximum will be presented. These descriptive statistics will be determined for measured values and for differences to baseline.

Descriptive statistics for categorical data

Absolute frequencies (N) will be presented with 0, relative frequencies (%) with at least 1 decimal. For changes from baseline, shift tables may be generated.

Inferential statistics

If not stated otherwise all statistical tests will be performed as described in the corresponding sections below.

All p-values will be rounded to 4 decimals (p<0.0001 will be displayed if the p-values are less than 0.0001). Unless otherwise specified, statistical significance will be declared if the rounded p-value will be less than 0.05.

All confidence intervals (CI) will be derived two-sided and at a confidence probability of $1-\alpha = 0.95$.

Listings

All subject data will be listed by subject. Identification variable will be the subject ID (composed of study, center and subject number separated by a hyphen, e.g. '31-01-01'). Any derived data listed will also be stored permanently and will be calculated as outlined in section 6.1 of this SAP.

Statistical Analysis Plan	Version 6.0		
Sponsor	Octapharma	Protocol No	WIL-31

4.1 Conventions

4.1.1 Baseline definition

Assessments at screening visit or the first IVR measurement (at PK or IVR visit, respectively) whatever is closest to start of prophylaxis are considered as baseline.

4.1.2 Missing data

In case of missing body weight documentation, data will be imputed using the Last Observation Carried Forward (LOCF) approach to calculate the dose per kg body weight (IU/kg).

In case of missing date/time documentations for IVR and PK samplings the corresponding scheduled time point will be used for analysis.

No further imputations for missing data will be performed.

Calculations pertaining to the derivation of annual bleeding rates will be based on documented time periods only.

4.1.3 Pooling of centers

All tables will be presented in total over all participating countries and centers. The distribution of number of subjects per country and center will be presented in the disposition section of the report.

4.1.4 Use of measurements from on-demand non-interventional run-in study (WIL-29)

Apart from analyzing the efficacy of Wilate in the prophylactic treatment of VWD based on annualized bleeding rates, it is also of interest to compare data with annualized bleeding rated of the same patients under an on-demand treatment schedule. To achieve this, data from those patients that also participated in a previous on-demand run-in study (WIL-29) will be used in the analysis data for the current study. This includes duration of On-demand phase, number of bleeding episodes and annualized bleeding rates for total, spontaneous, traumatic, and heavy menstrual bleeds.

For females with childbearing potential, it is of interest to compare their differences in median PBAC scores under prophylaxis with scores under on-demand treatment. For this purpose, all total PBAC scores collected during study WIL-29 will be stored in the WIL-31 database and the Wilcoxon matched pair sign-rank test will be used for statistical comparison.

The statistical methods for such exploratory comparisons of on-demand to prophylactic treatment schedule will be based on paired, or repeated-measurement data.

4.2 Demographic and other background data

The disposition of subjects (cf. Section 3) will be tabulated for the entire population. Details on protocol deviations will be listed.

Discontinued subjects will be described by frequency distributions including the reasons and in individual listings.

Statistical Analysis Plan	Version 6.0		Page 12 of 24
Sponsor	Octapharma	Protocol No	WIL-31

Demographic data (age, weight, height, BMI, race, ethnic group) will be summarized in tables and presented for the SAF, FAS and mFAS population. Other baseline or background data, e.g. disease-specific information, will comprise descriptive tables for the SAF and FAS population for the following variables:

- ABO blood group
- VWF:Ac and FVIII levels at screening, VWF multimer pattern for VWD type 2A, and genotype for VWD type 2B
- Vital Signs (Systolic and diastolic blood pressure, pulse, respiratory rate, and body temperature) at screening
- Physical examination (normal/abnormal) at screening
- Results of Parvovirus B19 antibodies at baseline IVR visit
- Urine pregnancy test (in female patients of child-bearing potential)
- Historical annual bleeding rates (ABR)
- Hemophilia Joint Health Score (HJHS) at baseline
- Target joint(s) at baseline

Historical PBAC scores (total scores documented under on-demand treatment from run-in study WIL-29)

4.3 IMP exposure, compliance

Prophylactic treatment will be administered 2 – 3 times per week at a dose of 20 – 40 IU/kg BW for 12 months.

In case of unacceptably frequent spontaneous breakthrough BEs (i.e., more than 2 spontaneous BEs or 1 major spontaneous BE within a 30-day period), the dose of *Wilate* should be increased by approximately 5 IU/kg (depending on the entire content of the additional vial(s) that need(s) to be reconstituted).

Overall summaries will be provided for

- Number of Injections
- Number of Exposure Days
- Total Dose (IU)
- Dose (IU/kg.)
- Reason for Administration

For the FAS and the mFAS population the following parameters will be summarized by frequency tables of descriptive statistics:

- Number of subjects treated prophylactically among all enrolled subjects
- Treatment regimen, dosage, changes, or interruptions in prophylactic treatments
- Number of injections
- Overall period of exposure (from first- to last dose of IMP)
- Number of exposure days

Statistical Analysis Plan	Version 6.0		Page 13 of 24
Sponsor	Octapharma	Protocol No	WIL-31

- Amount (IU) of *Wilate* used (per month, per year, exposure day and injection, and in total)
- Normalized dose (IU/kg) of *Wilate* used (per month, per year, exposure day and injection, and in total)
- Frequency and relative magnitude of dose changes: increased and decreased doses of *Wilate* used to treat individual BEs
- Frequency and relative magnitude of dose changes: in the doses per injection and changes in the total dose used to treat subsequent BEs of the same site (e.g. elbow, knee, etc.) in the same patient

All IMP treatment details will be listed for the FAS population.

Furthermore, the *Wilate* batches and their actual potencies will be included in the listing of individual doses.

4.4 Medical history, physical examination

Data on medical history will only be listed. Medical history will be coded according to the Medical Dictionary for Regulatory Activities (MedDRA). Codes will be reviewed by a Medical Expert and approved by the sponsor before data base lock.

4.5 Prior and concomitant medication

Any relevant medication taken at time of screening and all new medications taken by the subject during the study period are defined as 'Concomitant'. Any changes of medications during the study period will also be recorded.

All details of concomitant medications will be listed including, the route, dose, frequency, start and stop date and indication.

Concomitant medications will be coded using the WHO Drug Global thesaurus in the version current at the time of study start. Coding will be performed by the CRO and agreed upon with the sponsor before data base lock. (cf. DMP). For concomitant medications tables will show the frequencies of subjects by WHO Drug Global preferred term.

4.6 Concomitant non-pharmacological measures, pre-medication

Not applicable.

4.7 Efficacy

The analysis of the efficacy of prophylactic treatment with *Wilate* will be based on the FAS, mFAS and additionally on the PP set if the latter populations differ by >5% of the mFAS.

The efficacy of *Wilate* in prophylactic treatment will be presented based on the total annualized bleeding rate (TABR) – see section 4.7.1.

Primarily, all obtained data on treatment characteristics (IMP dosages, frequencies, total consumption) and BEs (duration, frequency, efficacy assessment) will be described by providing summary statistics.

Statistical Analysis Plan	Version 6.0		Page 14 of 24
Sponsor	Octapharma	Protocol No	WIL-31

4.7.1 Primary Endpoint

Primary objective of this study is to demonstrate that the total annualized bleeding rate (TABR) during prophylactic treatment lowers the patients' TABR during on-demand treatment by more than 50%.

TABR will be calculated as the total number of spontaneous, traumatic and other bleeds (excluding menstrual bleeds) in the time period between first prophylactic dose of IMP and the day of the last dose of IMP (+ 2 days wash-out), divided by the duration (in years) between first dose of prophylactic IMP and the day of last dose of IMP (+ 2 days wash-out). Surgery periods, and BEs occurring within these periods, will be excluded from the calculation of TABR. Menstrual bleeds of any severity will not be included in this calculation. In female patients with child-bearing potential heavy menstrual bleeds will be reported and analyzed separately.

For this efficacy assessment the individual annualized bleeding rates under prophylactic treatment in this study will be compared to the annualized bleeding rates recorded for the same patient during a previous, non-interventional study, (WIL-29).

To test whether the mean TABR during prophylactic treatment ($TABR_{pr}$) is less than half the historical mean TABR during on-demand treatment ($TABR_{od}$), the following pair of hypotheses will be tested in the context of negative binomial counting regression model:

$$(*) H_0: \text{mean}(TABR_{pr} / TABR_{od}) \geq 0.5 \quad \text{vs} \quad H_1: \text{mean}(TABR_{pr} / TABR_{od}) < 0.5$$

at a one-sided alpha level of 2.5%. A corresponding two-sided 95% CI for the different TABRs and their ratio will also be provided.

4.7.2 Secondary Endpoints

Secondary endpoints are:

- Spontaneous annualized bleeding rate (SABR), calculated in analogy with TABR
- Incremental IVR of Wilate for VWF:Ac (VWF:Rco and VWF:GP1bM) and FVIII:C (OS and CHR) over time (at baseline and at 1, 2, 3, 6, 9, and 12 months of treatment)
- For paediatric patients, baseline PK profile characteristics of VWF:Ac (VWF:Rco) and FVIII:C (OS and CHR) based on blood samples taken pre-dose and 1, 3, 9, 24, 48, and 72 hours after dosing
- Wilate consumption data (VWF/FVIII IU/kg per month per patient) for prophylaxis

The statistical analysis of the secondary endpoints will be descriptive, including exploratory 95% confidence intervals.

For the secondary endpoint SABR descriptive statistics will be tabulated. Comparisons with on-demand treatment similar to TABR analysis will be performed.

Regarding the IMP administration data, the following parameters will be listed:

- Dates and times of IMP injections
- Doses of IMP in IU and IU/kg and IMP batch numbers
- Reason for IMP injection (prophylaxis, treatment of BE, surgery)

Statistical Analysis Plan	Version 6.0		Page 15 of 24
Sponsor	Octapharma	Protocol No	WIL-31

Descriptive statistics will be determined for time in study, exposure days, number of infusions and dosages of IMP overall and by reason for IMP injection.

Descriptive statistics including changes to pre-infusion will be tabulated for VWF:Ac (VWF:Rco and VWF:GP1bM) at baseline IVR visit, at 1, 2, 3, 6, 9 months IVR visit and at study completion visit.

At the end of each BE treated with Wilate, treatment efficacy will be assessed by the patient (together with the investigator in case of on-site treatment). The efficacy assessment of treatment of BEs includes the categories 'excellent', 'good', 'moderate' and 'none'. All efficacy ratings assessed as either 'excellent' or 'good' will be considered 'successfully treated.'

Efficacy in the surgical prophylaxis

Efficacy in surgical prophylaxis will be analyzed descriptively, presenting summary tables and listing on all aspects of surgical treatment and procedures as well as efficacy ratings.

The following surgery-related parameters will be presented:

- Location, severity (minor or major, for definitions see protocol), and type (planned or emergency) of surgery
- Expected and actual duration of surgical procedure
- Expected average/maximum and actual blood loss
- Pre-, intra-, and/or postoperative IMP administration data (only listed)
- Pre-, intra-, and postoperative FVIII:C and VWF:Ac plasma levels (dependent on the availability of data)
- Routine safety laboratory
- Details on concomitantly administered products, except standard anesthetic products (only listed)
- Blood transfusion requirements (only listed)
- Brief narrative describing the outcome of the intervention (only listed)
- Assessment of efficacy of surgical prophylaxis:
 1. at the end of surgery by the surgeon
 2. at end of the postoperative period by the hematologist
 3. overall efficacy assessment taking both the intra- and postoperative assessments into account, assessed by the Investigator.
- Number of successfully treated surgeries ('excellent' or 'good' overall efficacy rating)

Procedures that meet the following criteria are considered as 'major' surgeries. All other procedures are considered 'minor'

- General or spinal anaesthesia required
- Opening into the great body cavities required
- Severe haemorrhage during surgery possible
- Haemostatic therapy for at least 6 days required
- Orthopaedic interventions involving joints (ankle, knee, hip, wrist, elbow, shoulder)
- 3rd molar extraction or extraction of ≥ 3 teeth
- Surgeries/conditions in which the patient's life is at stake

Time periods relative to surgical procedures are defined as:

Statistical Analysis Plan	Version 6.0		Page 17 of 24
Sponsor	Octapharma	Protocol No	WIL-31

- Preoperative is defined as the time period of up to 3 hours before the start of surgery.
- The end of surgery is defined as the time immediately after the last surgical suture.
- Postoperative is the period from the end of surgery to the time the patient returns to his or her regular Wilate treatment regimen.

QoL questionnaires

The results for the QoL scales (PROMIS-29, SF-36; SF-10 for patients <16 years of age) and different categories will be scored according to the analysis manual. Summary tables will be provided for baseline, 6-months and 12-months visit including changes to baseline.

HJHS questionnaires

The results for the HJH-scores over time will be summarized in descriptive tables for each visit including changes to baseline.

PBAC score (only female patients)

For female patients, the results of the PBAC score over time will be summarized in descriptive tables for each complete menstrual cycle. Additionally, the differences in intra-individual median PBAC scores under prophylaxis will be compared with scores under on-demand treatment (see also section 4.1.4).

Annualized rate of heavy (i.e. major) menstrual bleeds

For the exploratory endpoint Annualized rate of heavy menstrual bleeds descriptive statistics will be tabulated. The annualized rate of heavy menstrual bleeds will be calculated in analogy with TABR.

If possible, the annualized rates of heavy menstrual bleeds under prophylactic treatment in this study will be compared to the annualized rates of heavy menstrual bleeds recorded for the same patient during the previous, non-interventional run-in study.

4.8 Pharmacokinetics / Pharmacodynamics

For IVR assessments VWF:Ac (VWF:Rco and VWF:GP1bM) and FVIII:C (measured by both, the chromogenic (CHR) and one-stage assay (OS)) will be analyzed based on actual IMP potency.

Incremental IVR of *Wilate* over time (at baseline, 1, 2, 3, 6, 9 and at 12 months of treatment) will be analyzed in summary tables for each time point. For IVR analysis at baseline the IVRs derived from the paediatric PK profiles will also be included.

For children aged 6 to < 16 concentration versus time profiles will be obtained for VWF:Ac (VWF:Rco and VWF:GP1bM) and FVIII:C (OS and CHR) assays.

Calculation of PK parameters will be based on actual IMP potencies, on concentrations adjusted for residual pre-dose levels and actual time after end of infusion.

The following PK parameters will be derived from the adjusted concentration profiles.

:

Statistical Analysis Plan	Version 6.0		Page 18 of 24
Sponsor	Octapharma	Protocol No	WIL-31

- Area under the curve (AUC) and AUC normalized for the administered dose (AUC_{norm})
- In vivo half-life (T_½)
- Maximum plasma concentration (C_{max})
- Time to reach maximum plasma concentration (T_{max})
- Mean residence time (MRT)
- Volume of distribution (Vd)
- Clearance (CL)
- Incremental in vivo recovery (IVR)

The PK profiles and the PK parameters derived from them will be summarized by descriptive statistics (including geometric means and standard deviations, except for T_{max}) as well as the presentation of concentration vs. time plots. All derived PK parameters will be presented in by-patient displays.

PK profiles will additionally be presented graphically on original as well as semi-logarithmic scales as concentration-time curves, individually in spaghetti plots, and overall, showing the sample characteristic by time-point.

As PK data are only collected for children, the mentioned PK results will be presented in total and separately by age groups ('6 to <11' and '12 to <16' years) as well as by VWD type.

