Determination of Sample Size Assuming a mean TABR ratio (TABR _{pr} / TABR _{od}) of 0.25 with a correlation of 0.5 between the two treatment regimens, a coefficient of variation of 10 in on-demand treatment, and a coefficient of variation of 10 in prophylactic treatment, 25 patients will be needed to reject the null hypothesis with a power of 80% using a paired t-test for log-transformed data The primary approach to statistical analysis will be descriptive, complemented by exploratory confidence intervals (CIs) for means or proportions. Efficacy of Prophylactic Treatment with Wilate The primary endpoint of this study is to demonstrate that the TABR during prophylactic treatment with Wilate lowers the patients' TABR observed during on-demand treatment by more than 50%. To test whether the mean TABR during prophylactic treatment (TABR _{pr}) is less than half the mean TABR during on-demand treatment (TABR _{od}), the following pair of hypotheses will be tested using a paired t-test assuming log-normally distributed data: $H_0: \text{mean(TABR}_{\text{pr}} / \text{TABR}_{\text{od}}) \geq 0.5 \text{ vs } H_1: \text{mean(TABR}_{\text{pr}} / \text{TABR}_{\text{od}}) < 0.5$ at a one-sided alpha level of 2.5%. Corresponding two-sided 95% CIs for TABR will also be presented. To assess the qualitative robustness of the inferential result the hypothesis will additionally be tested with the Wilcoxon (matched-pair signed rank) test on the log-transformed bleeding rate as a distribution-free alternative. Also, a 95% Hodges-Lehmann CI for the median difference will be reported. In addition, intra-individual comparisons with each patient's documented historical TABR will be performed.

Name of Sponsor/Company: Octapharma AG	
Name of Investigational Product: Wilate	Protocol Identification Code: WIL-31
Name of Active Ingredient: Factor VIII/VWF concentrate human	Date of Final Protocol: 01-Mar-2021

Efficacy of *Wilate* in the Treatment of BEs

To assess the haemostatic efficacy of *Wilate* in the treatment of breakthrough BEs, a frequency distribution of all successfully treated BEs will be presented overall and by severity, along with an exploratory 95% CI. Statistical analyses of other secondary endpoints will be descriptive, including exploratory 95% CIs.

IVR Assessments

The results of IVR assessments over time will be presented per time point and as differences to baseline, along with 95% CIs for the mean differences.

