Concomitant medications	7.1.2	x	x	x	x	x	x	x	x	x	x	x	x	x	x

FLOW CHART FOR PK ASSESSMENT AND PROPHYLACTIC TREATMENT (PAEDIATRIC PATIENTS)—Continued

IVR = in vivo recovery, VWD = von Willebrand disease, VWF:Ac = VWF activity, GP1b = glycoprotein 1b, FVIII = factor VIII, FVIII:C = factor VIII procoagulant activity, OS = one-stage assay, CHR = chromogenic assay, PBAC = Pictorial Blood Loss Assessment Chart, PROMIS = Patient-Reported Outcomes Measurement System, SF-36v2 = 36-Item Short Form Health Survey (version 2), SF-10 = 10-Item Short Form Health Survey

LEGEND TO THE FLOW CHART FOR PK ASSESSMENT AND PROPHYLACTIC TREATMENT (PAEDIATRIC PATIENTS)

- * **COMPLIANCE CALL:** monthly telephone calls to take place ± 1 week to review compliance with completing diary, obtaining PBAC (for female patients of child-bearing potential), adherence with infusion regimen, AEs, and concomitant medications (see **Section 6.1.11**)
- (•) If inhibitor development is suspected
- [1] Before injection
- [2] Within 60 min before and 60 ± 5 min after injection
- [3] Blood samples for PK assessment to be taken within 60 min before injection and 60 ± 5 min, 3 h (± 30 min), 9 ± 1 h, 24 ± 2 h, 48 ± 2 h, and 72 ± 2 h after injection (central laboratory)
- [4] Before injection, if sample at the Baseline PK Visit was negative, or if it was equivocal on both original and re-testing
- [5] Before starting any other visit assessment
- [6] Target joint(s) are defined as having 3 or more spontaneous bleeding episodes into a single joint within 6 consecutive months preceding the Baseline Visit or the Study Completion Visit.
- [7] In female patients of child-bearing potential

FLOW CHART OF ASSESSMENTS FOR SURGICAL PROPHYLAXIS

Assessment	For details, see Section	Within 12 hours before start	Within 3 hours before start	Surgery		POP day 1	Any POP day	End of POP period
				Intra- operatively	End [1]			
Body weight		x						
Type of surgery	7.2.4	x						
Location of surgery	7.2.4	x						
Severity of surgery	7.2.4	x						
Expected duration of surgery	7.2.4	x						
Actual duration of surgery	7.2.4				x			
Expected average/maximum blood loss during surgery	7.2.4	x						
Actual blood loss and transfusions during surgery	7.2.4				x			
Administration of Wilate	7.2.1		x	(x)	(x)	(x)	(x)	(x)
FVIII:C plasma levels	7.2.4		# L	(#) L	(#) L	(#) [2] L	(#) L	(#) L
VWF:Ac plasma levels	7.4.5		# L	(#) L	(#) L	(#) [2] L	(#) L	(#) L
Routine safety laboratory	7.4.5	x				(x)	(x)	(x)

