3.1.2 Secondary Endpoints

The secondary endpoints of this study are the:

- Spontaneous annualised bleeding rate (SABR), calculated in analogy with TABR
- Incremental IVR of *Wilate* for VWF:Ac (VWF:RCO and VWF:GPIbM) and FVIII:C (OS and CHR) over time (at baseline and at 1, 2, 3, 6, 9, and 12 months of treatment)
- For paediatric patients, baseline PK profile characteristics of VWF:Ac (VWF:RCO) and FVIII:C (OS and CHR) based on blood samples taken pre-dose and 1, 3, 9, 24, 48, and 72 hours after dosing
- Safety and tolerability of *Wilate* by monitoring adverse events (AEs) throughout the study
- *Wilate* consumption data (VWF/FVIII IU/kg per month per patient) for prophylaxis

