6.1.2 Baseline IVR Visit (Adult Patients)

During the Baseline IVR Visit, the prophylactic dose and dosing interval of *Wilate* for each adult patient will be determined by the Principal Investigator based on the patient's clinical condition, and the first prophylactic dose will be administered after a washout period of **at least 72 hours** from the patient's latest administration of a VWF-containing product. Patients must not be experiencing any bleeding.

The following assessments will be performed:

BEFORE ANY OTHER ASSESSMENTS

- **Confirm inclusion and exclusion criteria** (to be documented in patient records)
- **QoL questionnaires** (PROMIS-29 for all patients, SF-36v2 or SF-10 as applicable)

BEFORE INJECTION

- **Weight**
- **Blood samples**
 - VWF multimer pattern for VWD type 2A and genotype for VWD type 2B [central lab]
 - Anti-parvovirus B19 antibodies [central lab]
 - Retention samples for possible virus marker and VWF/FVIII inhibitor testing [central lab]

WITHIN 60 MIN BEFORE AND 60±5 MIN AFTER INJECTION

- **Vital signs**
- **Blood samples**
 - VWF:Ac (VWF:RCO and VWF:GPIb) for IVR [central lab]
 - FVIII:C (OS and CHR) for IVR [central lab]

ANY TIME

- **Patient diary review, with documentation of PBAC** data and calculation of PBAC score by investigator (in female patients of child-bearing potential)
- **Hemophilia Joint Health Score (HJHS)**
- **Target joint(s)**
- Re-confirm commitment to using **birth control measures** (in female patients of child-bearing potential)
- Monitoring of **adverse events (AEs)**
- **Concomitant medications**

In adult patients, the first prophylactic injection of *Wilate* is administered during the Baseline IVR Visit.

In case of **home treatment**, patients will be trained in how to correctly administer the IMP and provided with IMP. Patients will be re-supplied with IMP whenever necessary during the study.

SCREENING AND BASELINE VISITS FOR PAEDIATRIC PATIENTS (6–16 YEARS)

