Sponsor	Octapharma	Protocol No	WIL-31

Variable	Description
ED	Exposure day = each calendar day the subject received IMP
C ₀	Last concentration before IMP administration
C _{max}	Maximum plasma concentration. Maximal measured concentration after end of IMP infusion (peak concentration)
T _{max}	Time to reach C _{max} (Timing starts at end of injection)
T _{1/2}	$\text{In vivo half-life } T_{1/2} = \frac{\ln(2)}{K}$ 
K = elimination rate constant, determined as the slope of the regression line) using linear regression on the terminal phase of the logarithm of the concentration

AUC	Area under the curve from baseline to infinity $AUC = \sum \left(\frac{(C_n + C_{n+1})}{2} \cdot \Delta t \right) + \frac{C_{last}}{K}$ 
(C_{last} is the last available measurement)

AUC _{norm}	AUC normalized for the administered dose
AUMC	Area under the moment curve (from baseline to infinity) $AUMC = \sum \left(\frac{(t_n \cdot C_n + t_{n+1} C_{n+1})}{2} \cdot \Delta t \right) + \frac{C_{last}}{K^2} + \frac{t_{last} \cdot C_{last}}{K}$
MRT	Mean residence time $MRT = \frac{AUMC}{AUC}$
CL	Clearance $CL = \frac{D}{AUC}$ where D is the actual dose administered
Vd	Volume of distribution at steady state: $Vd = CL \cdot MRT$
Incremental in vivo recovery (IVR)	$IVR = \frac{(C_{max} - C_0) \cdot BW}{D}$ 
where BW = body weight in kg and D = dose of IMP

Hemostatic success (in treatment of bleeding episodes and surgeries)	Success: efficacy rating is 'excellent' or 'good' Non-Success: efficacy rating 'moderate' or 'none' or 'missing'
Duplicate test results	If more than one blood sample for the same time point and test has been taken and two valid results are available/have been captured into the database, the mean of the values will be used in analysis

Statistical Analysis Plan	Version 6.0		Page 23 of 24
Sponsor	Octapharma	Protocol No	WIL-31

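### Children's baseline IVR is taken from an unwindowed Cmax over six PK samples, while every other IVR uses one 60-minute sample, so the baseline row mixes two rules

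*SAP*

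**What the plan says.** - **Formula.** SAP 6.1 gives the only IVR formula in the documents: (Cmax − C0) × body weight / dose. It defines Cmax as "Maximal measured concentration after end of IMP infusion (peak concentration") and sets no time window.
- **Children at baseline.** Protocol 3.1.2 describes the paediatric baseline profile as "based on blood samples taken pre-dose and 1, 3, 9, 24, 48, and 72 hours after dosing", so there are six post-dose values. SAP 4.8 then says: "For IVR analysis at baseline the IVRs derived from the paediatric PK profiles will also be included".
- **Adults at baseline, and everyone later.** Protocol 6.1.2 samples adults "WITHIN 60 MIN BEFORE AND 60±5 MIN AFTER INJECTION". The visits from month 1 to month 12 (Protocol 6.1.5 to 6.1.10) follow the same scheme at all ages. With one post-dose value, Cmax can only be that value.
- **Presentation.** Under SAP 4.8, IVR over time "will be analyzed in summary tables for each time point". The protocol's study outline has the results "presented per time point and as differences to baseline, along with 95% CIs for the mean differences". The SAP revision history for version 6.0 drops the change from baseline for IVR.
- **Pre-dose levels.** SAP 4.8 derives the PK parameters, IVR among them, from concentrations already adjusted for residual pre-dose levels. The formula in SAP 6.1 also subtracts C0.

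Neither document limits the paediatric baseline IVR to the 60-minute sample.

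**The concern.** The maximum of several noisy measurements tends to exceed a single measurement at a fixed time, even when the true level is highest at that time. Under the SAP's definitions, children's baseline IVR is such a maximum, while their IVR at months 1 to 12 is a single value. Adult baseline IVR is also a single value, and SAP 4.8 puts adults and children in one baseline row.

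IVR over time is a named secondary endpoint, and its use is to show whether recovery stays stable over a year. A rule that lifts only the first point can look like a small decline in recovery. Children are a sizeable part of that row: at least 12 of about 40 patients in Protocol 3.2 (30%), and at least 10 of 28 in SAP 1.5 (36%).

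**Working it through.** The documents state no IVR figure, so there is none to reproduce.

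**1. Direction of the sampling rule alone.** The six post-dose values include the 1 h value. Hence max(C1, C3, C9, C24, C48, C72) ≥ C1 in every child. With C0, body weight and dose held fixed, the Cmax-based IVR is never below the 60-minute IVR.

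**2. Size per child.** This needs a half-life and an assay CV, which the documents do not give. Assumed ranges are 12–25 h and 5–15%. The model is mono-exponential decline from 1 h with log-normal error, 400,000 simulated profiles per setting. Bias = mean(maximum of six) / mean(1 h value) − 1.

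| Half-life | CV | Bias, six samples | Bias, 1 h and 3 h only | Maximum not at 1 h |
|---|---|---|---|---|
| 12 h | 5% | 0.14% | 0.14% | 5% |
| 12 h | 10% | 1.5% | 1.5% | 21% |
| 12 h | 15% | 3.7% | 3.6% | 29% |
| 25 h | 5% | 0.9% | 0.9% | 22% |
| 25 h | 10% | 3.3% | 3.2% | 36% |
| 25 h | 15% | 6.35% | 5.8% | 44% |

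The range is about 0.1–6.4%. Nearly all of it comes from the 3 h sample. The 9 h sample is the maximum in at most 7% of profiles, and the samples from 24 h on in under 0.01%.

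Sensitivity: if true levels were flat between 1 and 3 h, the bias would be 2.8% at a CV of 5%, 5.6% at 10% and 8.7% at 15%.

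**3. Size in the pooled baseline row.** If children and adults have the same average IVR, pooled bias = share of children × bias per child.
- Lower end: 0.30 × 0.14% = 0.04%.
- Upper end: (10/28) × 6.35% = 2.3%.

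**4. A possible effect in the other direction.** If the profile is already reduced by the pre-dose level and the formula then subtracts C0 again, the relative change in IVR is −C0 / (dose × rise per IU/kg). Inputs are the 60 IU/kg PK dose (Protocol 5.4.1), the 1.5–2% rise per IU/kg (Protocol 5.4.3) and an assumed C0 of 10%:
- rise of 2%: 10 / (60 × 2) = 8.3% lower;
- rise of 1.5%: 10 / (60 × 1.5) = 11.1% lower.

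With C0 = 0 the change is zero. At C0 = 10%, a double subtraction would exceed every upward figure in the table.

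**The case against.** **The SAP does not plan the affected comparison.** Version 6.0 drops the change from baseline for IVR, and neither document lists IVR over time by age group. What remains is a reader looking down the rows of a descriptive table. This stands in part. The rows still sit side by side, and the protocol still plans differences to baseline with confidence intervals.

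**The planned row is pooled, so the per-child figure overstates what would be seen.** This stands. The pooled effect is about 0.04–2.3%, and the full per-child figure applies only to a children-only trend.

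**The inputs are assumed.** This stands. Across the assumed ranges the effect runs from negligible to modest.

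**The effect can be found in the outputs.** Cmax and Tmax are displayed by patient, so a reader can see which children peaked after 1 h. This is true, but the IVR table would remain uncorrected.

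**Stronger readings are tempting.** A reader might infer that baseline IVR is biased upward overall and that any later fall is false. The documents do not support that: a double subtraction of C0 would lower children's baseline IVR, and the text does not settle whether C0 is removed once or twice. Children's baseline dose (60 ± 10 IU/kg) also differs from the prophylactic dose at later visits (20–40 IU/kg), so the sampling rule is not the only difference between those rows. A reader might also expect a larger bias for FVIII:C through a later peak. The documents give no figure for that, and it is not claimed here.

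**Conclusion.** The point holds in a limited form. As written, the plan puts two IVR estimators under one label in the baseline row. The sampling rule by itself can only raise the paediatric values, by about 0.1–6.4% per child and about 0.04–2.3% in the pooled mean. These figures rest on assumed CVs of 5–15%, assumed half-lives of 12–25 h, mono-exponential decline from 1 h and 30–36% children.

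The rule can produce a small apparent fall in the by-visit tables, and in the differences to baseline if those are reported as the protocol plans. The net direction stays open until the handling of C0 is stated. IVR is a descriptive secondary endpoint without a test, and the primary bleeding-rate analysis does not use it. Priority is low.

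**What to change.** In SAP 4.8 and 6.1:

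- State that every IVR in the over-time tables, including the paediatric baseline, is (60 ± 5 min concentration − pre-dose concentration) × body weight / dose.
- State that these are unadjusted concentrations, so that C0 is subtracted exactly once.
- Keep Cmax-based recovery in the PK parameter table only, under a separate name, and say there too whether C0 has already been removed from the profile.
- Reconcile the protocol and the SAP on whether IVR differences to baseline are reported.

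The 60-minute and pre-dose samples are already in the paediatric PK schedule. The cost is a few lines of SAP text and one derivation in the analysis program, with no new data. The difference in sampling rule then becomes zero by construction.
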